6.3.1.2 Changes from Baseline

In all seizure analyses, the Baseline (Core) value will be the baseline used. These analyses exclude the subjects from Study ZX008-1504 Cohort 1. For any of the variables defined in the previous section, the change from baseline for any individual subject will be calculated as

$$\text{CCSF} = \text{Post-baseline value} - \text{CSF}_{\text{BC}}$$

The percentage change from baseline for any individual subject will be calculated as

$$\text{PCCSF} = (\text{Post-baseline value} - \text{CSF}_{\text{BC}}) * 100 / \text{CSF}_{\text{BC}}$$

The key effectiveness measures are CSF_{E1} and CSF_{E2} . Summary statistics for the changes from baseline and the percentage changes from baseline will also be presented. A Wilcoxon signed rank test will be used to assess the significance of the change from baseline. Given that baseline refers to the period prior to initiation of double-blind treatment in the Core study, it is expected that long-term treatment with ZX008 will lead to a reduction in convulsive seizure frequency. If we designate the mean baseline (core) CSF by μ_{BC} , and the mean for CSF_{E1} and CSF_{E2} by μ_{E1} and μ_{E2} , respectively, the key effectiveness objective is to test the null hypothesis

$$H_0: \mu_{\text{E1}} - \mu_{\text{BC}} = 0,$$

Against the alternative

$$H_A: \mu_{\text{E1}} - \mu_{\text{BC}} \neq 0,$$

Rejection of the null hypothesis in favor of the alternative, in the presence of a statistically significantly smaller mean convulsive seizure frequency during OLE Treatment (two-sided p-value < 0.05) will be regarded as evidence of a treatment benefit.

In a similar manner, each of the changes over time will be summarized and assessed for statistical significance.

The summary statistics and statistical testing will also be presented by age group.

A graph of the CSF for baseline (Core), Core Study (T+M), and during OLE Month 1 ...36 will be generated, and another graph of the percentage changes from baseline may be plotted.

6.3.1.3 Treatment Group Estimates – Endpoint Analyses

The analysis of covariance (ANCOVA) analyses described in this section exclude de novo subjects. The convulsive seizure frequency per 28 days during the entire OLE Treatment period and the convulsive seizure frequency per 28 days during Month 2 to EOS, CSF_{E1} and CSF_{E2} , respectively, will each be analyzed using an ANCOVA model with age group (<6 years, ≥6 years) and treatment group (4 levels) as factors, and CSF_{BC} and CSF_{CTM} as continuous covariates. The goal of this analysis is to estimate the seizure frequency during (1) the entire OLE treatment, and (2) during Month 2 to EOS, for each of the treatment groups included in the OLE, after adjusting for the other factors in the model. To avoid taking the logarithm of 0, a value of 1 will be added

to a covariate and/or response prior to taking logs. From the general linear model, least squares estimates of treatment means and the corresponding 95% confidence intervals, will be exponentiated and a value of 1 subtracted from the result, (to offset the addition of 1 prior to taking logs), in order to provide estimates and associated 95% confidence intervals on the original scale for the response variable.

Since the ANCOVA relies on assumptions of normality, the analysis will be repeated using a nonparametric method that does not require as stringent assumptions. A nonparametric ANCOVA will be used to analyze the data, with ranks of the CSF_{BC}, and ranks of the CSF_{CTM} as covariates and ranks of the response (CSF_{E1} or CSF_{E2}); other terms/factors in the model will be the same as for the parametric ANCOVA.

Due to certain portions of the core studies remaining blinded, the ANCOVA analyses described in this section will not be submitted with the Japanese interim analysis.

6.3.1.4 Treatment Group Estimates – CSF Over Time

The general linear mixed effects model with repeated measures (i.e. MMRM) described in this section exclude de novo subjects. Analyses will be performed for the convulsive seizure frequency per 28 days, over time. In these analyses, the CSF_{CSFW} will not be included in the model. A MMRM will be employed to estimate the mean convulsive seizure frequency per 28 days, over time, for each treatment group. The model will include CSF_{BC} and CSF_{CTM} as fixed covariates; time (14 levels for Month1, Month2, Month3, Month 4-6, Month 7-9, Month 10-12, Month 12-15, Month 16-18, Month 19-21, Month 22-24, Month 25-27, Month 28-30, Month 31-33, and Month 34-36) as a fixed effect; age stratum (2 levels) as a fixed effect; treatment group (4 levels) as a fixed effect; and subject as a random effect.

CSF will be log transformed prior to analysis, and a value of 1 may be added to avoid taking the logarithm of 0.

The purpose of this modeling is to obtain least-squares adjusted means over time for the frequency of convulsive seizures per 28 days along with 95% confidence intervals.

While we seek to estimate the means over time, the variances and covariances are nuisance parameters and need to be estimated to provide associated standard errors for the treatment estimates. For the MMRM, an unstructured covariance matrix will be used. [If the model experiences convergence issues, a different covariance structure may be explored from the available choices in SAS PROC MIXED, and the covariance structure with the smallest AIC will be chosen.]

The model adjusted means and associated confidence limits will be plotted against time.

Furthermore, exploratory analysis will be carried out using a general linear model that includes the mean daily dose during OLE period (categorized as low, medium, and high) as explanatory variable, and the same factors used in the MMRM described above.

Due to certain portions of the core studies remaining blinded, the MMRM analyses described in this section will not be submitted with the Japanese interim analysis.

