Least Squares Mean[2]	XX.X	XX.X	XX.X	XX.X	XX.X
95% CI[2]	(XX.X,XX.X)	(XX.X,XX.X)	(XX.X,XX.X)	(XX.X,XX.X)	(XX.X,XX.X)

.... (Repeat for months 2, 3, 6, 9, 12, 15, 18, 21, 24, 27, 30, 33,
and 36

mITT = Modified intent-to-treat population; CI = Confidence Interval; SD = Standard Deviation; SE = Standard Error.

Note: this table excludes de Novo subjects.

[1] Baseline and overall OLE values were log transformed prior to analysis. To avoid taking log of 0, a value of 1 was added to each subject's convulsive seizure frequency value (the response variable) for each timepoint in the OLE period before taking the natural logarithm.

[2] Results are based on a general linear model with fixed effects for treatment group (four levels excluding group that contained all subjects enrolled in 1503 – regardless of feeder study) and age group (< 6 years, ≥6 years), time (Months 1, 2, 3, 6, 9, 12, 15, 18, 21, and 24) and log baseline convulsive seizure frequency as a covariate; and random effects for subject (repeated over time). The dependent variable is log convulsive seizure frequency (overall OLE period) as response.

[3] Values obtained from the ANCOVA model were exponentiated to get the corresponding values on the original scale.

Programming note: Use PROC MEANS for summary stats

For MMRM model, use PROC MIXED. Before calling the PROC, please add 1 to the Month1, Month2, ... Month24 CSF values, then take the natural log (log to base e) of these values to be used in the model. PROC MMRM for parametric model analysis. The LSMeans are the LSMeans for the time*treatment interaction terms. See stats manual.

Programming Notes: Use the shell for 14.2.1.4 for

Table 14.2.1.5
Convulsive seizure frequency per 28 days, Over Time – Parametric Analysis Using Mean Daily Dose
mITT Population

In place of treatment groups, categorize subjects into three treatments depending on their mean daily dose during the OLE Treatment period as Low, Medium, and High. See SAP.

Categories for Low, Medium, High depending on the following doses of ZX008

<0.4 mg/kg = Low

0.4-0.6 mg/kg = Medium

>0.6 mg/kg = High

[figure not shown]
Table 14.2.1.6
% of Subjects with Changes in AED medications during 1st 6 months of OLE Treatment Period
mITT Population

OLE Period	PBO-ZX008 OL (N = XX)	ZX 0.2 – ZX008 OL (N = XX)	ZX 0.5 – ZX008 OL (N = XX)	ZX 0.8 – ZX008 OL (N = XX)	ZX008 OL (N = XX)
Any Change in AED medication during the 1 st 6 months	XX (XX%)	XX (XX%)	XX (XX%)	XX (XX%)	XX (XX%)

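### The over-time seizure model in SAP 6.3.1.4 lacks the group-by-time term that its output table needs, its shell disagrees with the text, and adjusting for core-study seizure frequency changes what the group means describe.

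*SAP*

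**What the plan says.** SAP 6.3.1.4 states the aim of the repeated-measures model: "A MMRM will be employed to estimate the mean convulsive seizure frequency per 28 days, over time, for each treatment group". Its fixed effects are the covariates CSF_BC (core baseline) and CSF_CTM (core titration plus maintenance), "time (14 levels for Month1, Month2, Month3, Month 4-6" and so on through Month 34-36, age stratum, and "treatment group (4 levels) as a fixed effect; and subject as a random effect". No product of treatment group and time is listed. On covariance it says: "For the MMRM, an unstructured covariance matrix will be used".

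The shell for Table 14.2.1.4 (Appendix 1) describes the analysis differently in three places:

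- The programming note says: "The LSMeans are the LSMeans for the time*treatment interaction terms".
- Footnote [2] lists ten time points ending at Month 24 and log baseline as the only seizure covariate. It has neither an interaction nor CSF_CTM. The instruction to add 1 before taking logs also ends at Month 24, although the table body repeats through Month 36.
- Footnote [3], which also stands under Table 14.2.1.2, says: "Values obtained from the ANCOVA model were exponentiated to get the corresponding values on the original scale".

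The endpoint ANCOVA in 6.3.1.3 uses age group and treatment group as factors, "and CSF_{BC} and CSF_{CTM} as continuous covariates". For the return to the original scale it states that results "will be exponentiated and a value of 1 subtracted from the result".

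**The concern.** A model with main effects of time and group lets the groups differ by one constant amount on the log scale. It cannot show whether the feeder groups start apart and converge, or the reverse, which is what estimates over time by group are for. A programmer who follows 6.3.1.4 cannot fill Table 14.2.1.4 as its note directs. One who follows the note must fit a model that the SAP does not state, and must then choose between two time ranges and two covariate lists.

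CSF_CTM is measured while subjects are on their randomized feeder treatment, so it is partly a result of the group factor in the same model. LS means are evaluated at one common value of it. They therefore describe groups imagined to have had the same seizure rate in the core study, not the open-label frequency each group had.

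At stake are Tables 14.2.1.2, 14.2.1.4 and 14.2.1.5 and Figure 14.2.1.8 (model-adjusted means), in the final report.

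**Working it through.** The SAP gives no figure of its own on this point, so there is none to reproduce.

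**1. Parameter count (6.3.1.4).** 4 groups × 14 intervals = 56 means. Main effects supply 1 + (14 − 1) + (4 − 1) = 17 parameters. The missing interaction has (14 − 1) × (4 − 1) = 39 degrees of freedom. Age stratum and the covariates, entered as main effects, do not alter the shape of any group's profile.

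**2. Text against shell.**

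| Item | SAP 6.3.1.4 | Shell 14.2.1.4 |
|---|---|---|
| Group by time | not listed | absent from footnote [2]; required by programming note |
| Time levels | 14, to Month 36 | 10, to Month 24 (footnote); Month 36 (table body) |
| Seizure covariates | CSF_BC and CSF_CTM | log baseline only |
| Return to original scale | not described | exponentiate only |

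**3. Back-transformation.** The response is ln(CSF + 1). A value of 2 is analysed as ln 3, and exp(ln 3) = 3, so without the subtraction it prints 50% too high. A value of 4 prints as 5 (+25%). Every estimate and confidence limit is too high by exactly 1.

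**4. Effect of CSF_CTM.** If β is the slope of log open-label CSF on log CSF_CTM within groups, and Δ is the difference in mean log CSF_CTM between placebo and 0.8 mg/kg at equal baseline, adjustment multiplies the placebo/0.8 ratio by exp(−βΔ). The SAP gives neither β nor Δ, so both are assumed:

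- β = 0.3, Δ = 0.3: exp(−0.09) = 0.91
- β = 0.7, Δ = 0.7: exp(−0.49) = 0.61
- β = 0.9, Δ = 1.0: exp(−0.90) = 0.41

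**5. Simulation check.** Group sizes come from SAP Table 1: 120 placebo, 80 at 0.2, 40 at 0.5 and 80 at 0.8. There were 200 data sets with 14 intervals and complete data, fitted by least squares on the log scale without the +1 and without age. Assumptions: core log effects 0, −0.3, −0.5, −0.7; SDs 0.8 (baseline), 0.5 (persistent subject deviation), 0.3 (core noise) and 0.4 (open-label noise). These imply β = 0.25/(0.25 + 0.09) = 0.735 and a shift of exp(−0.735 × 0.7) = 0.60.

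Scenario A: all groups have identical open-label rates. Scenario B: the log difference between placebo and 0.8 is 0.40 in Month 1, 0.25 in Month 2, then 0. Entries are placebo/0.8 ratios at Month 1 / Month 34-36.

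| Model | A (true 1.00 / 1.00) | B (true 1.49 / 1.00) |
|---|---|---|
| Main effects, with CSF_CTM (6.3.1.4) | 0.60 / 0.60 | 0.62 / 0.62 |
| Main effects, without CSF_CTM | 1.00 / 1.00 | 1.04 / 1.04 |
| Group × time, with CSF_CTM | 0.60 / 0.60 | 0.90 / 0.60 |
| Group × time, without CSF_CTM | 1.01 / 1.01 | 1.50 / 1.00 |

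The 1.04 in scenario B is close to the plain average: (0.40 + 0.25)/14 = 0.046, and exp(0.046) = 1.05. Only the last row recovers both truths.

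**The case against.** The strongest reply is that the missing interaction is a drafting gap. The programming note can be carried out only if the term is in the model, so a programmer working from the shell would add it. It is true that 6.3.2.5 writes out an age-by-time interaction for seizure-free days, but the matching footnote to Table 14.2.5.2 omits that one, so absence from a list in this SAP does not prove intent. This stands as an account of how the gap arose. It does not remove it, because the SAP and the footnote both state a model that cannot give the table's output.

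On CSF_CTM, the covariate precedes open-label Day 1 and 6.3.1.3 openly seeks adjusted estimates, so the result is a legitimate conditional quantity. The shells print group LS means, not ratios or differences. That also stands. The difficulty is that the conditional means are presented as each group's open-label frequency.

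Some stronger readings are tempting but unsupported:

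- That open-label Month 1 is when former 0.8 mg/kg subjects step down and placebo subjects start drug. SAP 3.2 places the move to 0.2 mg/kg in the core transition period, before open-label Day 1. Scenario B is therefore only an illustration.
- That 6.3.1.4 itself prescribes the wrong back-transformation. It says nothing about exponentiation. The incomplete instruction is in the shell footnotes, and for Table 14.2.1.2 the text of 6.3.1.3 is correct.
- That the model is not identifiable. A random intercept added to an unstructured 14 × 14 matrix (14 × 15/2 = 105 parameters) would be redundant, but footnote [2] of Table 14.2.1.4 describes subject as repeated over time, so the wording may be shorthand for the repeated unit.

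**Conclusion.** The point holds. As listed, the 6.3.1.4 model forces parallel log-scale profiles and cannot produce the LS means that Table 14.2.1.4 calls for. That follows from the text alone, as do the conflicts over time range and covariates and the missing subtraction of 1.

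The CSF_CTM effect rests on assumptions for its size. Its direction needs only a core-study benefit of active drug and a positive slope: adjustment then favours the former placebo group. With the values tried, groups with equal open-label rates would show a placebo/0.8 ratio between 0.41 and 0.91, and 0.60 in the simulated case.

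The interaction point concerns 6.3.1.4 only, since the 6.3.1.3 ANCOVA has one value per subject and no time factor. A reader might infer that the trial's effectiveness conclusions are undermined, and the SAP does not support that. The primary objective is safety, the key effectiveness test in 6.3.1.2 is a within-group signed rank test that none of this touches, unadjusted CSF by group and interval appears in Table 14.2.1.1.1, and between-group results are declared descriptive in 6.1.1. Severity: should-fix, before the final analysis.

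**What to change.** 1. In 6.3.1.4, add treatment group by time to the fixed effects and state that the LS means come from that term.
2. In the Table 14.2.1.4 footnote and its add-1 note, use the 14 intervals through Month 36 and the same covariate list as 6.3.1.4.
3. In Tables 14.2.1.2, 14.2.1.4 and 14.2.1.5, report exp(LSM) − 1 and transform the confidence limits in the same way. Say so in 6.3.1.4 too.
4. In 6.3.1.3 and 6.3.1.4, make the main group estimates without CSF_CTM. If the adjusted version is kept, label it as a conditional or sensitivity analysis at a common core-study rate.
5. State that subject is the repeated unit for the unstructured matrix, not an added random intercept.

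The cost is wording in two SAP sections and the related shells. No new data are needed. Dropping CSF_CTM makes the residual variance slightly larger, so intervals widen a little. The 39 interaction degrees of freedom also have to be estimated, which is unavoidable if the table is to show each group over time.

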6.3.1.5 Seizure Frequency by Dose

Additional analyses will be performed to examine the convulsive seizure frequency over time, reported as per 28 days, by the actual dose administered.

Subjects will be grouped into low, medium, and high dose groups depending on their mean daily dose of ZX008 during the OLE Treatment period:

- Low: 0.2 to <0.4 mg/kg
- Medium: 0.4 to <0.6 mg/kg
- High: >0.6 mg/kg.

The parametric ANCOVA for the endpoint analysis will be repeated using these three dose groups in place of the four treatment groups, excluding de novo subjects.

Similarly, a nonparametric ANCOVA will be performed using these dose groups, excluding de novo subjects.

Due to certain portions of the core studies remaining blinded, the ANCOVA analyses described in this section will not be submitted with the Japanese interim analysis.

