3.2 TREATMENTS

Subjects in the double-blind studies Z008-1501, -1502, and cohort 2 of 1504 who enter Study ZX008-1503 would have transitioned to 0.2 mg/kg during the transition period (between Visits 12 and 13), as described in the 1501 and 1502 Clinical Study Protocols Section 5.5.5, and 1504 Sections 5.5.6 and 5.5.7. Subjects entering from Cohort 1 in Study ZX008-1504 will enter a transition period at a fixed dose of ZX008 0.2 mg/kg/day for up to 24 additional weeks.

In Study ZX008-1503, during the OLE Treatment Period, all subjects will be treated initially with 0.2 mg/kg/day for 1 month to assess effectiveness of this dose in all study subjects. After 1 month at a dose of 0.2 mg/kg/day, the investigator may adjust the dose of each subject based on effectiveness and tolerability. Subjects whose condition worsened relative to their status at the end of the double-blind feeder study could request permission to increase to 0.4 mg/kg/day (max 30mg) after approximately 2 weeks on the 0.2 mg/kg dose. Dose changes should be made in increments of 0.2 mg/kg/day, to a maximum of 0.8 mg/kg/day but not to exceed total dose of 30 mg/day. Dose increases should not occur earlier than every 14 days at each dose level. For subjects in Study ZX008-1504 Cohort 2, the dose titration schedule is 0.2 mg/kg/day, to 0.4, to 0.5 not to exceed 20 mg/day. Dose increases may only occur after a review of the diary and reported AEs, and if, in the investigator's opinion, seizure frequency, severity, and/or duration indicates a change in medication regimen is warranted. Dose decreases for tolerability can occur at the investigator's discretion, in dose amounts and frequency appropriate for the situation. ZX008 dose adjustments outside of these parameters should be discussed with the Medical Monitor prior to initiation.

Effectiveness and safety data will be provided for all subjects treated with ZX008. Data will be summarized by subjects' treatment group in their previous study.

The treatment groups that may be used to summarize the results of the final analysis are presented in Table 1. Groups 1 to 5 are the basic treatment groups.

Table 1. Treatment Groups in Study ZX008-1503 According to Treatment in Feeder Study

Name of Treatment Group	Treatment Group Code	AED Treatment from Feeder study	Feeder Study(s)	Approximate Total Number of subjects at Final Analysis

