3.4 RANDOMIZATION AND BLINDING

This is an open-label study and the doses to be administered are ZX008 0.2 mg/kg to 0.8 mg/kg up to a maximum of 30 mg/day. Subjects taking concomitant STP, including subjects from Study ZX008-1504, should not exceed 0.5 mg/kg/day; with a daily maximum of 20 mg. Assignment of subject to treatment is not randomized. All subjects begin the OLE treatment period with 0.2 mg/kg for one month, after which the dose may be adjusted in increments of 0.2 mg/kg to achieve appropriate level of effectiveness/tolerability.

This document cannot be used to support any marketing authorization application and any extensions or variations thereof.

PUBLIC COPY

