Programming note: Need to use exposure data to determine mean daily dose during OLE for each subject, and categorize each subject as having had Low, Medium or High dose of ZX008 as follows:

0 – <0.4 mg/kg = Low;

0.4 – 0.6 mg/kg = Medium;

>0.6 mg/kg = High

Programming note: Use the shell for Table 14.2.1.1.3 for

Table 14.2.1.1.8

Convulsive seizure frequency per 28 days during OLE Treatment Period Using Mean Daily Dose: Summary Statistics and Tests of Changes from Baseline
mITT Population (Japan)

Table 14.2.1.1.4
Convulsive seizure frequency per 28 days during OLE Treatment Period Using Mean Daily Dose, by Age Group: Summary Statistics and Tests of Changes from Baseline
mITT Population

Programming Note: Repeat 14.2.1.1.3 for Age groups <6, and ≥6.

Add Header, top left, prior to the table proper, “Age Group: <6 years” or “Age Group: ≥6 years”.

Programming Note: Use the same shell fo produce

Table 14.2.1.1.9
Convulsive seizure frequency per 28 days during OLE Treatment Period Using Mean Daily Dose, by Age Group: Summary Statistics and Tests of Changes from Baseline
mITT Population (Japan)

Table 14.2.1.1.5
 Convulsive seizure frequency per 28 days during OLE Treatment Period: Summary Statistics
 Subjects from 1504 Cohort 1

	ZX008 OL[1] (N = XX)
Core Study Day 2 through End of PK Follow-up Period *	
N	XX
Mean (SD)	XX.X (XX.XX)
Median	XX.X
Min, Max	XX.X, XX.X
Core Study Transition Period**	
N	XX
Mean (SD)	XX.X (XX.XX)
Median	XX.X
Min, Max	XX.X, XX.X
Month1 (OLE)	
N	XX
Mean (SD)	XX.X (XX.XX)
Median	XX.X
Min, Max	XX.X, XX.X
Month2 (OLE)	
N	XX
Mean (SD)	XX.X (XX.XX)
Median	XX.X
Min, Max	XX.X, XX.X
.....	
Repeat for Month3, Month6, Month9, Month12, Month15, Month18, Month21, Month24, Month 27, Month 30, Month 33, Month 36	
ENDPOINT1: Overall OLE Treatment Period	
N	XX
Mean (SD)	XX.X (XX.XX)
Median	XX.X
Min, Max	XX.X, XX.X

	ZX008 OL[1] *(N = XX)
ENDPOINT2: Month02-EOS	
N	XX
Mean (SD)	XX.X (XX.XX)
Median	XX.X
Min, Max	XX.X, XX.X

Notes:

[1]Subjects were on open-label ZX008 0.2 mg/kg during the entire 6 months of the Transition Period. Starting from Day 1 in the OLE Period, their dose was set at 0.2 mg/kg for the first month, and subsequently adjusted by the PI to achieve optimal dose for effectiveness/tolerability.

*For most subjects this ends on Day 15; for some subjects the PK Period ends on Day 14 or Day 16.

**Transition Period starts 1 day after end of PK Follow-up Period and ends 1 day prior to OLE Visit 1 Day 1.

Table 14.2.1.2

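### One Low/Medium/High label per subject, taken from mean mg/kg over the whole OLE, does not show seizure frequency by dose received and ties dose group to response, STP use, weight and, in short follow-up, time on study

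*SAP*

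**What the plan says.** SAP 6.3.1.5 announces an analysis of CSF over time according to administered dose, then defines the groups by a single average: "Subjects will be grouped into low, medium, and high dose groups depending on their mean daily dose of ZX008 during the OLE Treatment period". The bands are "Low: 0.2 to <0.4 mg/kg", "Medium: 0.4 to <0.6 mg/kg", and High above 0.6 mg/kg. It adds that "The parametric ANCOVA for the endpoint analysis will be repeated using these three dose groups in place of the four treatment groups". The programming note to shell Table 14.2.1.1.3 says the same, its list closing with the third group: "Need to use exposure data to determine mean daily dose during OLE for each subject, and categorize each subject as having had Low, Medium or". The definition carries into Tables 14.2.1.1.3-4, their Japan versions 14.2.1.1.8-9, and Tables 14.2.1.5 and 14.2.5.3.

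The dosing rules are in 3.2, 3.3.1 and 3.4. Subjects begin at 0.2 mg/kg/day. "After 1 month at a dose of 0.2 mg/kg/day, the investigator may adjust the dose of each subject based on effectiveness and tolerability". Those who worsened relative to the end of the feeder study may ask to go to 0.4 after about two weeks. "Dose increases should not occur earlier than every 14 days at each dose level". An increase requires that, in the investigator's opinion, seizures call for it. Without stiripentol (STP) the ceiling is 0.8 mg/kg/day and 30 mg/day. With it: "Subjects taking concomitant STP, including subjects from Study ZX008-1504, should not exceed 0.5 mg/kg/day; with a daily maximum of 20 mg".

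**The concern.** A label averaged over the whole period is fixed only when follow-up ends, yet the shells apply it to every interval from Month 1 onward. Shell Table 14.2.1.1.3 prints a Month 1 row, with a p-value, under a High column, although in Month 1 subjects are at or near 0.2.

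The label also depends on the response. Persistent seizures lead to a higher dose, a higher dose moves the subject to a higher group, and CSF over those same days is what the group is used to summarise. Even with no dose effect at all, subjects who respond poorly would collect in the higher groups. Time on study, STP use and weight enter the label as well. At stake is the reading of every by-dose CSF table, ANCOVA and MMRM, because differences between columns may reflect any of these rather than dose.

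**Working it through.** The plan gives no figure of its own on this point to reproduce. The check applies its dosing rules to its cut-points of 0.4 and 0.6 mg/kg.

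**Month 1.** On the standard rule the 30-day mean is 0.20. Under the two-week exception, with further 14-day steps, it is (14×0.2 + 14×0.4 + 2×0.6)/30 = 9.6/30 = 0.32. Both are below 0.4, so within the stated rules no subject is at a Medium or High average in Month 1.

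**Time on study (no STP, weight not limiting).** The fastest standard path is 0.2 on Days 1-30, 0.4 on Days 31-44, 0.6 on Days 45-58, and 0.8 from Day 59. The shortfall from 0.8 is 30×0.6 + 14×0.4 + 14×0.2 = 26.4, so for T > 58 the mean is 0.8 − 26.4/T.

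| Day T | Mean (mg/kg) |
|---|---|
| 66 | 0.40 |
| 90 | 0.507 |
| 132 | 0.60 |
| 1095 | 0.776 |

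Other paths:
- Two-week exception: shortfall 14×(0.6 + 0.4 + 0.2) = 16.8. The mean reaches 0.6 at Day 84 and is 0.613 at Day 90.
- Steps at Months 1, 2 and 3: shortfall 30×(0.6 + 0.4 + 0.2) = 36. The mean reaches 0.6 at Day 180.
- Steps at Months 1, 3 and 6: shortfall 30×0.6 + 60×0.4 + 90×0.2 = 60. The mean reaches 0.6 at Day 300.

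The effectiveness population (5.3) needs only 30 days of seizure data, so early leavers are included.

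**STP.** The 0.5 mg/kg ceiling is below 0.6, so High is out of reach while on STP. On the fastest path the shortfall from 0.5 is 30×0.3 + 14×0.1 = 10.4. The mean 0.5 − 10.4/T reaches 0.4 at Day 104.

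**Weight.** Without STP, 30/0.6 = 50 kg and 30/0.4 = 75 kg. A subject who stays above 50 kg cannot exceed 0.6, and one who stays above 75 kg is below 0.4. With STP, 20/0.4 = 50 kg, above which the full 20 mg/day is below 0.4.

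**Adjustment.** The ANCOVA in 6.3.1.3, reused in 6.3.1.5, has two age strata, baseline CSF and core-study CSF. It has no term for weight, STP or follow-up.

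**Bands.** In 6.3.1.5 a mean of exactly 0.6 belongs to no group, nor does a mean below 0.2. The latter can occur, since 3.3.1 recalculates dose only after a 25% weight change. The first header of shell Table 14.2.1.1.3 has Medium as 0.4 to 0.6 and High as 0.6 or more, so 0.6 falls in both. Its later headers and footnote have High above 0.6 and Low from just above zero.

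**The case against.** The strongest reply is that these analyses are labelled additional or exploratory. SAP 6.1.1 makes between-group intervals and p-values descriptive, no formal comparison is planned, and nowhere does the plan claim a dose-response. That stands and limits the severity. However, the caution in 6.1.1 about confounding is directed at within-treatment change from baseline and does not mention dose groups.

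A reader might infer that the starting month and the caps largely determine the groups, or that Low and Medium consist mainly of early leavers and heavy subjects. The SAP gives no weight distribution or dropout rate, so neither can be shown. The first month at 0.2 is not universal, and for long follow-up its effect is small: 30 days at 0.2 instead of 0.8 lower the mean by 18/1095 = 0.016 at Day 1095. On the fastest standard path a subject at 0.8 is still Low only on Days 59-65.

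Nor are capped subjects misclassified: someone above 75 kg on 30 mg/day really does receive less than 0.4 mg/kg. The limits also hold only while weight and STP use stay as they are. Children grow, and 6.3.1.6 lets background AEDs be withdrawn after six months.

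Baseline and core-study CSF adjust in part for earlier response, but not for response during the OLE. Tables 14.1.5.1.8.1 and 14.1.5.1.9.1 cross dose with duration, which exposes the link, but for the Safety Population, with other bands and without CSF.

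For Japan, Month 3 is a minimum follow-up, and the by-dose ANCOVA and the MMRM are withheld. By-dose summary Tables 14.2.1.1.8 and 14.2.1.1.9 are still flagged for that report. Finally, the footnote bands in shell Table 14.2.1.1.3 do cover every value; the problem is that the SAP text and the first header differ from them.

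**Conclusion.** The concern holds in a limited form. The whole-period mean does not deliver what 6.3.1.5 sets out to show: early intervals appear under doses not yet given, and group membership depends on the outcome. In short follow-up it also depends on time on study. On the fastest standard titration a subject at 0.8 from Day 59 is not above 0.6 until after Day 132 and averages 0.51 at Day 90, which bears on the Japan summary tables for subjects near the minimum follow-up. For an uncapped completer at 0.8 this is negligible (0.776). STP use and weight are confounded with dose group at any length of follow-up and are unadjusted.

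These figures assume the titration schedules shown, full dosing and stable weight and STP status. They show who is affected, not how many. The harm is to interpretation of descriptive tables, not to a formal test. The change should be made, but the study's main conclusions do not depend on it. The band conflict needs correcting in any case.

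**What to change.** 1. In the by-interval rows of Tables 14.2.1.1.3-4 and 14.2.1.1.8-9, and in the by-dose MMRMs (Tables 14.2.1.5 and 14.2.5.3), classify each Table 7a interval by the actual mg/kg dose in force at its start, after applying the mg/day cap. The assigned dose is already needed for Table 14.1.5.1.7.1, but that nominal level must be converted for capped subjects.
2. Show results separately with and without concomitant STP.
3. Remove the by-dose ENDPOINT1 and ENDPOINT2 rows and the whole-period by-dose ANCOVAs. Otherwise keep them with a label saying they are confounded by titration to response, follow-up and STP use and are not a dose-response.
4. Use one exhaustive, non-overlapping set of bands in 6.3.1.5 and every shell. The boundary at 0.6 will matter more once intervals are classified by current dose, because 0.6 is itself a titration level.

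The cost is SAP wording and reprogramming from data already held. The downsides are smaller cells, a Month 1 that is almost entirely Low, and loss of comparability with the 2018 interim tables. Some confounding remains, since the dose at the start of an interval still reflects earlier seizures.
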